5.2 EXCLUSION CRITERIA

Participants who meet any of the following criteria will be excluded from the study:

1. Known allergy to insulin.
2. Preexisting diabetes.
3. Current or previous use of diabetes medication or insulin.
4. Any nasal disease or congestion that may interfere with intranasal drug absorption.
5. Baseline hypoglycemia (blood glucose \leq 65 mg/dL) or hyperglycemia (blood glucose > 200 mg/dL) as evident from the screening labs.
6. Active serious disease, such as liver disease, kidney disease, uncontrolled hypertension, clinically significant hypokalemia, and significant or unstable medical illness
7. Blood donation in excess of 500 mL within 60 days prior to the first dose of study medication.
8. Treated with an investigational drug within 30 days.
9. Individuals with inadequate venous access.

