Description of Study Intervention:	HUMULIN R U-500 (insulin human injection, Eli Lilly, NDC 0002-8501-01) to be given intranasally at differing doses depending on study day. Sterile diluent to prepare the zero insulin dose and lower concentrations of intranasal insulin will also be acquired through Eli Lilly (NDC 0002-0800). A total of 11 possible doses will be tested, ranging from 0 to 1000 U insulin. Each volunteer will come for 5 visits.
Study Duration:	One year
Participant Duration:	Up to 60 days from the day of screening to last visit.

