1.3 SCHEDULE OF ACTIVITIES (SOA)

Schedule of Events table						
Study Visits	Screening	1	2	3	4	5
Study Day(s)	-28	0	7+/-3	14+/-3	21+/-3	28+/-3
Provide study overview and participant responsibilities	X					
Informed consent	X					
Medical history and inclusion/exclusion criteria review	X					
Previous and concomitant medications	X	X	X	X	X	X
Physical examination	X					
Vital signs ¹	X	X	X	X	X	X
Urine pregnancy test (female subjects of child bearing potential)	X	X	X	X	X	X
Insertion of a short term intravenous catheter		X	X	X	X	X
Study drug administration ²		X	X	X	X	X
Clinical laboratory screening labs ³	X					
POC serum glucose ⁴		X	X	X	X	X
Serum C-Peptide ⁵		X	X	X	X	X
Serum Insulin ⁵		X	X	X	X	X
Adverse event reporting		X	X	X	X	X

¹ Vital signs include blood pressure, pulse rate, respiration rate, and temperature at supine position.

² Study drug will be administered intranasally.

³ Clinical laboratory screening labs include clinical comprehensive metabolic panel and CBC.

⁴ Point-of-care (POC) serum glucose glucometry will be performed at 0, 15, 30, 60, 120, 180, and 240 minutes after each intranasal insulin administration. Sample will be collected +/- 10 minutes of scheduled assessment.

⁵ Blood and plasma samples will be collected, aliquoted, and frozen at 0, 15, 30, 60, 120, 180, and 240 minutes after each intranasal insulin administration for blood insulin and C-Peptide measurements by the University of Michigan Pharmacokinetics Core. Sample will be collected +/- 10 minutes of scheduled assessment.

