3 OBJECTIVES AND ENDPOINTS

OBJECTIVES	ENDPOINTS	JUSTIFICATION FOR ENDPOINTS
Primary		
Determine the maximum tolerated dose of intranasal insulin in healthy participants	Primary endpoint: The primary safety outcome will be severe hypoglycemia as defined by blood glucose <45mg/dL at any post administration glucose check during a study visit.	The American Diabetes Association defined severe hypoglycemia as “severe cognitive impairment requiring external assistance for recovery” without assigning a blood glucose cutoff (12). As such, we chose blood glucose < 45mg/dL as the cutoff for severe hypoglycemia based on prior clinical studies (13).
Secondary		
Characterize the pharmacokinetics and pharmacodynamics (PK-PD) of intranasal insulin in healthy participants	Secondary endpoints will include the change in blood glucose, insulin, and C-peptide levels for up to 4 hours after drug administration to evaluate for any systemic absorption of intranasal insulin.	Prior studies have not characterized the PK-PD of conventional insulin formulation doses above 160 U administered intranasally.

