6.1.2 DOSING AND ADMINISTRATION

Rules for assigning patients

Within subject rules (subject progressing through tiers for cohort):

1. If a volunteer experiences severe hypoglycemia (blood glucose <45 mg/dL), they will be assigned a dose 100 U less for the next round and for all subsequent rounds.
2. If a volunteer experiences severe hypoglycemia a second time, they will be withdrawn from the study.

Study wide rules (determine which dose tiers are allowable for all future volunteers):

1. All doses from 0 to 1000 U by increments of 100 U will be eligible for testing in the study.
2. If there is greater than 0.9 probability that a dose has a greater than 0.1 toxicity rate, that dose will be removed for all future cohorts (see below).

Allocation Rules

Initial Allocation and Strategy:

Overall, the philosophy of allocation is to assign as many patients as possible to higher doses, while also limiting exposure to toxic doses. The trial will start the first cohort with 200, 400, 600, 800, and 1000 U.

Allocation Adjustment Rules:

After each hypoglycemic event, we will recalculate the toxicity probabilities for that dose to see if a dose removal threshold has been met.

If a dose meets the criteria for removal, that dose and all higher doses will be removed from future participants and cohorts. For the next cohort or patient within a cohort, the highest additional doses available will be used. For example, if 700 U was removed, then 200, 300, 400, 500, 600 U would be the new future allocation.

If a cohort completes with no observed episodes of dose-limiting toxicity (DLT), the smallest (and any smaller) doses will drop, and the highest unused dose will replace it. For example, after zero episodes of DLT in Cohort 1 at any dose, Cohort 2 will use 400, 600, 800, 900, and 1000 U. Doses 100 and 200 U will be dropped.

If a cohort has any DLT, but no dose is dropped (only 1 DLT in two different doses for example), the initial allocation rules will be used for the next cohort (200, 400, 600, 800, 1000 U).

4 Cohort Example - No DLT (Demonstrated by Schema Figure 1.2.2)

Cohort 1: Participants #1 to 6

The doses will be 0, 200, 400, 600, 800, and 1000 U.

Cohort 2: Participants #7 to 12

If there were 0 events in Cohort 1, then the doses for Cohort 2 will be 0, 400, 600, 800, 900, and 1000 U. 200 U will be dropped and 900 U will be entered.

Cohort 3: Participants #13 to 18

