24	.0063	.1123	.3460	.6152	.8189	.9310	.9784	.9944	.9988	.9998	1.0000	1.0000	1.0000	1.0000	1.0000	1.0000	1.0000	1.0000	1.0000	1.0000	1.0000	1.0000	1.0000	1.0000	1.0000

In practice, this means if 2 DLTs are observed for a dose in the first cohort, the dose is dropped. To drop a dose in subsequent cohorts, see the shaded area of the above table. To delete a dose, one must have 3 total observed DLTs in Cohorts 1 and 2, or 4 total DLTs in Cohorts 1-3, or 5 total DLTs in Cohorts 1-4.

Rules for discontinuing or modifying the overall study

There are no binding rules to discontinue the overall study. However, if the 500 U dose tier was dropped, there would only be 100, 200, 300, and 400 U available. In this case, the PI will consult with the other investigators to present an amended plan for future study conduct or overall discontinuation.

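### No rule makes dosing depend on that day's glucose, and the 0-minute reading is not guaranteed to be taken before the dose

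*Combined protocol and SAP*

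**What the plan says.** **Eligibility.** Section 5.2, exclusion 5, rules out a glucose of 65 mg/dL or less, or "hyperglycemia (blood glucose > 200 mg/dL) as evident from the screening labs". The Schedule of Activities (Section 1.3) marks those labs once, at Day -28. Section 8.1.2 has the inclusion and exclusion criteria reviewed before procedures at study visits.

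**Glucose on the dosing day.** Schedule footnote 4 places point-of-care readings "at 0, 15, 30, 60, 120, 180, and 240 minutes after each intranasal insulin administration" and adds: "Sample will be collected +/- 10 minutes of scheduled assessment". At Visit 1 the first active dose follows a 0 U administration and its 4 hours of observation (Sections 4.1, 6.1 and 8.1.2).

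**Action on a low value.** Sections 2.3.3, 6.5.1 and 8.1.2 prescribe intravenous dextrose and food below 45 mg/dL. For values of 70 mg/dL or less but not below 45, they prescribe a repeat reading every 30 minutes until the value exceeds 70.

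**Endpoint and dose rules.** A DLT is a glucose below 45 mg/dL "at any post administration glucose check during a study visit" (Section 3). After one, "they will be assigned a dose 100 U less for the next round and for all subsequent rounds" (Section 6.1.2). Once a dose meets the removal criterion, "that dose and all higher doses will be removed from future participants and cohorts". Section 7.1 spells out the first-cohort case: "this means if 2 DLTs are observed for a dose in the first cohort, the dose is dropped".

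**Baseline.** Sections 9.1 and 9.4.3 analyse change in glucose from baseline, with baseline glucose as a covariate.

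**The concern.** Glucose is the primary safety variable, and the drug can lower it. The plan requires a negative pregnancy test before each dose in applicable participants, but it sets no corresponding condition on glucose. As written, someone who arrives at a level that would have barred enrolment can be given intranasal insulin at doses up to 1000 U. Section 3 notes that the pharmacology of conventional insulin above 160 U by this route has not been characterised.

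Low starts are plausible under the visit rules. Section 5.3 sets a minimum fast of 2 hours and no maximum. At Visit 1 no meal is mentioned between the 0 U run and the active dose, so the fast could reach 2 + 4 = 6 hours or more.

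Two further things are at stake. If the 0-minute sample is drawn after dosing, the baseline used in Sections 9.1 and 9.4.3 is not a clean pre-dose value. And a later reading below 45 mg/dL counts against the dose whatever the starting value. Without an assured pre-dose reading, a drug effect is hard to separate from a low start.

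**Working it through.** **1. Does any rule hold a dose on that day's glucose?**

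| Place | What it acts on | What it does | Withholds a dose? |
|---|---|---|---|
| 5.2, exclusion 5 | Screening labs | Bars enrolment | Not on dosing-day glucose |
| 8.1.2, criteria review | The listed criteria | Its only glucose criterion is exclusion 5, which points back to screening | No |
| 2.3.3, 6.5.1, 8.1.2 | Below 45; 70 or less | Treats; monitors | No |
| 6.1.2, 7.1 | DLTs | Reduces or removes doses | Only after a DLT |
| 7.2 | Investigator request | Stops treatment | Discretion, no threshold |

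**2. Timing of the 0-minute reading.** Window: 0 ± 10 minutes, so -10 to +10 minutes around the dose. Half of that window is after dosing.

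**3. How many doses depend on it.** Administrations: 24 × 6 = 144, of which 24 are 0 U and 24 × 5 = 120 are active. The 24 active doses at Visit 1 follow a same-day series of seven readings ending at 240 minutes, although no rule acts on that series. For the other 120 - 24 = 96 active doses, the 0-minute reading is the only scheduled same-day glucose that could precede the dose.

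**4. Age of the screening value.** Visit 1: 28 days. Visit 5 at the end of its window: 28 + 28 + 3 = 59 days. This agrees with the Synopsis limit: "Up to 60 days from the day of screening to last visit".

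**5. What DLTs do to a dose.** With k DLTs in n participants the posterior is Beta(0.2 + k, 0.8 + n - k). Recomputed probability that the DLT rate exceeds 0.1:

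- 1 of 6: Beta(1.2, 5.8), 0.6292
- 2 of 6: Beta(2.2, 4.8), 0.9196
- 1 of 24: Beta(1.2, 23.8), 0.1123

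All three match Table SB1A. Removal needs 0.9, so one event does not remove a dose, while two at the same dose in Cohort 1 do.

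**6. Chance of removal.** With looks at 6, 12, 18 and 24 participants and bounds of 2, 3, 4 and 5 DLTs, the Section 9.2 table is reproduced:

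| DLT rate | 0.01 | 0.025 | 0.05 | 0.075 | 0.10 |
|---|---|---|---|---|---|
| Chance of removal | 0.0016 | 0.0105 | 0.0467 | 0.1125 | 0.2062 |

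If low starts alone caused DLTs at an assumed 1%, 2.5% or 5% at an otherwise inert dose, the first three columns apply. If they added 2.5 or 5 points to an assumed true rate of 5%, removal would rise from 0.0467 to 0.1125 or 0.2062. The documents support none of these assumed rates.

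**7. The only external evidence in the documents.** Section 4.3 cites no hypoglycemia in 1,053 subjects at 20 to 160 U. The one-sided 95% upper bound is 1 - 0.05^(1/1053) = 0.0028, or 0.28%. At that rate the chance of removal is about 0.0001. This is indicative only, because the definition of hypoglycemia and any pre-dose checks in those studies are not given.

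**The case against.** The strongest reply is that the natural reading of 0 minutes is a baseline taken just before dosing. Footnote 4 applies one phrase and one window to all seven time points, and Section 3 confines DLTs to checks after administration. Intravenous access, serial readings, dextrose, medical staff on site and investigator discretion also limit the harm. The reported falls at 160 U, 0.2 to 0.4 mmol/L (× 18 = 3.6 to 7.2 mg/dL), are small against the fall of more than 20 mg/dL needed to go from 65 to below 45. If a higher dose did cause such a fall, it would be a drug effect and properly counted.

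Most of this stands, and it limits the weight of the point. It does not supply a rule. Even a reading taken before dosing changes nothing unless someone must look at it and has a value at which to stop.

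A reader might infer that the defect is a screening value up to 59 days old. The documents do not support that emphasis: exclusion 5 is an enrolment criterion, and a one-day-old value would not show arrival glucose either. A reader might also infer that low starts would materially pull down the maximum tolerated dose, with removal as high as 0.2062. That figure rests on assumed rates, and the cited record at lower doses points to much smaller ones.

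**Conclusion.** The gap is real. Under the readable text, a participant who arrives at or below 65 mg/dL can be dosed, and the 0-minute reading is not assured to be a pre-dose baseline. At Visit 1 the 0 U series gives same-day information before the active dose, but no rule uses it.

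This is chiefly a matter of participant safety and baseline timing. How often participants arrive low cannot be taken from the documents, so its effect on the trial's result cannot be computed. That effect is probably small: one event does not remove a dose (0.6292 at 1 of 6), and the first-cohort rule needs two events at the same dose (0.9196). The change is worth making because it is cheap and closes a plain safety gap, not because the maximum tolerated dose is shown to be at risk.

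**What to change.** In Section 8.1.2 and Schedule footnote 4:

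- Require the 0-minute glucose to be taken and read before every administration. At Visit 1 the 240-minute reading of the 0 U run may serve for the active dose, provided it is read first.
- Withhold the dose at 65 mg/dL or below, the protocol's own exclusion limit. A limit of 70 mg/dL, at which the protocol already starts 30-minute monitoring, is an acceptable stricter choice.
- Recheck the same day. If the value is still low, reschedule within the existing visit window or record the dose as not given. Visit 1 has no window, and one should not be added for its active dose, because that would separate the dose from its same-session 0 U control.
- State that the pre-dose reading is the baseline and not a DLT check.
- Leave a dose not given out of that dose's numerator and denominator.

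**Cost.** The change is protocol wording; all 144 zero-minute readings are already planned. An occasional dose will be delayed or missed, so the text should say whether a missed tier is repeated or skipped. Missing 400 U at Visit 2, for example, means either ending at 800 U or stepping from 200 to 600 U. With one of six participants missing at a dose, removal still needs two DLTs (n = 5: 0.6873 with one, 0.9454 with two). The results would describe participants who start above the chosen limit.

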5.3 LIFESTYLE CONSIDERATIONS

Nothing to eat or drink for at least 2 hours prior to each study visit.

Abstain from alcohol for at least 12 hours before the start of each dosing session.

5.4 SCREEN FAILURES

Individuals who do not meet the criteria for participation in this trial (screen failure) will not be rescreened given that this is a healthy participants study.

5.5 STRATEGIES FOR RECRUITMENT AND RETENTION

The University of Michigan maintains a database of healthy male and female volunteers (<https://www.umhealthresearch.org/>). The database includes approximately 40,000 volunteers. The initial strategy will include a targeting request to volunteers that are likely to meet inclusion criteria based on information stored in this database. Given the study plan to recruit up to 24 volunteers, it is highly likely that this approach will be sufficient. However, other strategies such as the use of Institutional Review Board's (IRB) approved flyers may be posted throughout the University of Michigan, Ann Arbor campus to solicit potential healthy volunteers. The scheduling of procedures will be carefully orchestrated by the study team to improve subject retention.

Participants will be compensated at the local competitive rate for healthy volunteers in phase I investigational drug studies. The full rate will be prorated over a maximum of 6 research visits (one screening visit and 5 study visits). Phone calls, texts, or email reminders will be sent ahead of their appointment dates.

5.6 CONSIDERATIONS RELATED TO COVID-19

To reduce risks to participants and study staff related to COVID-19 infection, the study will comply with institutional and governmental precautions and restrictions in place at the time the study is being conducted. In addition, the study will ask that all participants be vaccinated against COVID-19 prior to the first study visit. The study may also perform point-of-care screening for COVID-19 infection using a saliva test at the time of the study visits depending on community prevalence and contemporaneous guidance.

6 STUDY INTERVENTION

6.1 STUDY INTERVENTION(S) ADMINISTRATION

Regular insulin (Humulin R U500, Eli Lilly, Indianapolis IN) at a concentration of 500 U/mL will be used to create ≤ 2 mL doses containing between 0 – 1000 U. The ≤ 2 mL doses will be administered intranasally using a 5 mL syringe divided into ≤ 1 mL per nostril. Intranasal administration will be performed with the participants supine with the neck extended (a modified Mygind position)(19, 20, 21). to mimic the position of comatose OHCA patients. Participants will be instructed to sniff following intranasal administration and rest in supine position for 15 minutes.

A total of 11 possible doses will be tested, ranging from 0 to 1000 U insulin.

Each volunteer will come for 5 study visits. In the first visit, the volunteer is administered placebo. They will receive the first assigned intranasal insulin dose 4 hours later followed by another 4 hours of observation. During visits 2-5, they will receive additional escalating doses based on the dosing protocol.

6.1.2 DOSING AND ADMINISTRATION

Rules for assigning patients

Within subject rules (subject progressing through tiers for cohort):

1. If a volunteer experiences severe hypoglycemia (blood glucose <45 mg/dL), they will be assigned a dose 100 U less for the next round and for all subsequent rounds.
2. If a volunteer experiences severe hypoglycemia a second time, they will be withdrawn from the study.

Study wide rules (determine which dose tiers are allowable for all future volunteers):

1. All doses from 0 to 1000 U by increments of 100 U will be eligible for testing in the study.
2. If there is greater than 0.9 probability that a dose has a greater than 0.1 toxicity rate, that dose will be removed for all future cohorts (see below).

Allocation Rules

Initial Allocation and Strategy:

Overall, the philosophy of allocation is to assign as many patients as possible to higher doses, while also limiting exposure to toxic doses. The trial will start the first cohort with 200, 400, 600, 800, and 1000 U.

Allocation Adjustment Rules:

After each hypoglycemic event, we will recalculate the toxicity probabilities for that dose to see if a dose removal threshold has been met.

If a dose meets the criteria for removal, that dose and all higher doses will be removed from future participants and cohorts. For the next cohort or patient within a cohort, the highest additional doses available will be used. For example, if 700 U was removed, then 200, 300, 400, 500, 600 U would be the new future allocation.

If a cohort completes with no observed episodes of dose-limiting toxicity (DLT), the smallest (and any smaller) doses will drop, and the highest unused dose will replace it. For example, after zero episodes of DLT in Cohort 1 at any dose, Cohort 2 will use 400, 600, 800, 900, and 1000 U. Doses 100 and 200 U will be dropped.

If a cohort has any DLT, but no dose is dropped (only 1 DLT in two different doses for example), the initial allocation rules will be used for the next cohort (200, 400, 600, 800, 1000 U).

4 Cohort Example - No DLT (Demonstrated by Schema Figure 1.2.2)

Cohort 1: Participants #1 to 6

The doses will be 0, 200, 400, 600, 800, and 1000 U.

Cohort 2: Participants #7 to 12

If there were 0 events in Cohort 1, then the doses for Cohort 2 will be 0, 400, 600, 800, 900, and 1000 U. 200 U will be dropped and 900 U will be entered.

Cohort 3: Participants #13 to 18

If there were 0 events in Cohorts 1 and 2, then the doses for Cohort 3 will be 0, 600, 700, 800, 900, and 1000 U. 400 U will be dropped and 700 U will be entered.

Cohort 4: Participants #19 to 24

Same as Cohort 3.

Other situations (more than one DLT)

Please also refer below to rules for discontinuing a dose.

If a dose (or doses) is dropped during or after a cohort, the highest available unused doses will be used for the next patients within that cohort and the next cohort. For example, if 1000 U is dropped, the future doses will be 200, 400, 600, 800 and 900 U. Or, if 800 U and all higher doses are dropped, then 200, 400, 500, 600, and 700 U will be the next set.

As one example, if there is 1 DLT in a different dose in each of the 4 cohorts, the trial will simply allocate using the initial rules for all cohorts, with the exception of the within subject adjustment rule noted above.

For example, if there are no DLTs in Cohort 1, then Cohort 2 will use 400, 600, 800, 900, and 1000 U. If Cohort 2 also has no DLTs, then 300 and 400 U will drop and Cohort 3 will use 600, 700, 800, 900, and

1000 U. Even if there are no DLTs in Cohort 3 given that allocation, we will continue that allocation as it utilizes the 5 highest available doses.

If higher doses are dropped, they cannot be reconsidered in the study.

If lower doses are dropped, they can re-enter the study. This would occur if higher doses needed to be dropped by having DLTs over the threshold. The lower doses may need to re-enter in order for each subject to have 5 potential doses.

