7 STUDY INTERVENTION DISCONTINUATION AND PARTICIPANT DISCONTINUATION/WITHDRAWAL

7.1 DISCONTINUATION OF STUDY INTERVENTION

The rules for stopping or changing an individual dosing regimen are given above in the Dosing and Administration section.

Rules for discontinuing a dose

We are interested in proceeding with a dose if we remain confident that the Dose Limiting Toxicity (blood glucose < 45 mg/dL) is < 0.1 (1 in 10).

Using the Bayesian Toxicity Monitoring software from MD Anderson (<https://ibl.mdanderson.org/BTM/>)

We define Toxicity parameters as:

Probability of DLT is represented by θ

Maximum probability of DLT allowed (θ_{\max}): 0.1

When calculating the probability of DLT at a dose, we will use a Beta(0.2,0.8) prior. This is a vague prior with a median of 0.2 and a 95% credible interval from 0 to 0.94. There is greater density over probabilities of DLT near zero in this non-symmetric distribution. Each DLT is added to the A parameter of the beta distribution, and each patient who is DLT free is added to the B parameter of the B distribution. Therefore, with the prior included, if 24 participants have DLT on a dose, the probability of DLT can be described with a Beta(0.2,24.8) distribution. In this setting, the posterior estimate for DLT probability is 0.008 (or 0.8%). In addition, the probability that that dose has a DLT proportion over 0.1 is only 0.006 (or 0.6%).

$\text{Prob}(\theta > \theta_{\max}) \geq 0.9$ (Or that there is 90% or greater probability that the DLT is greater than 0.1)

We define the probability that $\text{Prob}(\theta > \theta_{\max})$ as the final output of the trial for each dose. For each dose, we will also calculate the probability that toxicity is greater than 0.1 at that dose.

The below table (SB1A) illustrates the probability that DLT is greater than 0.1 based on the number of observed events.

Table SB1A: Probability of Early Stopping
Number of Toxicities
(Highlighted = Prob(e > 0.1) >= 0.9)

	0	1	2	3	4	5	6	7	8	9	10	11	12	13	14	15	16	17	18	19	20	21	22	23	24
Number of Patients																									
6	.0884	.6292	.9196	.9990	.9993	1.0000	1.0000	NA	NA	NA	NA	NA	NA	NA	NA	NA	NA	NA	NA	NA	NA	NA	NA	NA	NA
12	.0333	.3613	.7196	.9151	.9816	.9971	.9997	1.0000	1.0000	1.0000	1.0000	1.0000	1.0000	NA	NA	NA	NA	NA	NA	NA	NA	NA	NA	NA	NA
18	.0141	.2027	.5135	.7773	.9220	.9786	.9954	.9992	.9999	1.0000	1.0000	1.0000	1.0000	1.0000	1.0000	1.0000	1.0000	1.0000	1.0000	1.0000	NA	NA	NA	NA	NA

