8.1.2 Study Visits

Participants (in cohorts of 6) will present to the Michigan Clinical Research Unit on their scheduled dosing day, and will be asked to have not consumed any food for at least 2 hours and any alcohol for at least 12 hours prior to this visit. A urine pregnancy test will be performed to rule out pregnancy prior to administration of the intranasal insulin dose to applicable female participants. The subject's total body weight and supine vital signs (heart rate, blood pressure, temperature, and respiratory rate) will be recorded. Eligible Participants will proceed with the study procedures after review of inclusion and exclusion criteria.

Participants will be asked to participate in 6 administrations over 5 sessions with a 1-week washout interval between each session. The first session will include an initial control administration of 0 U with 4 hours of observation, then followed by the first dose-escalation intranasal insulin administration and another 4 hours of observation. Subsequent visits will involve a single dose-escalation administration per visit as described in 6.1.2 Dosing and Administration. Any subject experiencing severe hypoglycemic episode will be given 100 U less than the last administered dose for the remainder of the study. Any participant having a second event, will be withdrawn from the study.

Participants will have peripheral intravenous access established with the placement of a short-term IV catheter for serial blood sampling and administration of supplemental glucose if needed. 5 mL of venous blood samples (3 mL as waste and 2 mL for blood glucose, insulin, and C-Peptide analyses) will be collected at 0, 15, 30, 60, 120, 180, and 240 minutes after each intranasal drug administration. Blood glucose levels will be measured with a point of care glucometer. The remaining blood samples will be centrifuged, aliquoted, and frozen for serum insulin and C-Peptide analyses by the University's Pharmacokinetics Core.

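### The dose-removal rule contradicts itself for tiers with fewer than six patients, and the 100 U reduction after a DLT creates such tiers

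*Combined protocol and SAP*

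**What the plan says.** **Within-subject rules.** Section 6.1.2 says that after severe hypoglycemia "they will be assigned a dose 100 U less for the next round and for all subsequent rounds". Section 8.1.2 fixes the reference point: "Any subject experiencing severe hypoglycemic episode will be given 100 U less than the last administered dose for the remainder of the study". A repeat event ends participation: "If a volunteer experiences severe hypoglycemia a second time, they will be withdrawn from the study".

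**Study-wide rule as a posterior.** Section 6.1.2: "If there is greater than 0.9 probability that a dose has a greater than 0.1 toxicity rate, that dose will be removed". The probability is recalculated after every event, for the dose of that event. The effect is wide: "If a dose meets the criteria for removal, that dose and all higher doses will be removed from future participants and cohorts". Section 6.1.2 also bars removed higher doses from returning. For the calculation, section 7.1 states "we will use a Beta(0.2,0.8) prior" and updates it so: "Each DLT is added to the A parameter of the beta distribution, and each patient who is DLT free is added" to the B parameter. No minimum number of patients is given.

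**Study-wide rule as counts.** Below Table SB1A, section 7.1 restates the rule as two DLTs at a dose in Cohort 1, three over Cohorts 1–2, four over Cohorts 1–3 and five over Cohorts 1–4. Section 6.1.2 gives single DLTs at two different doses as an example in which no dose is dropped and the initial allocation is used again.

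**Silence.** Table SB1A starts at six patients. The operating characteristics in 9.2 assume 24 observations on one dose. No section says whether reduced-dose rounds enter A and B, or whether a participant treated repeatedly at one tier counts once or once per administration. Sections 9.1 and 9.4.1 define the maximum tolerated dose by the posterior alone.

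**The concern.** The starting schedule is 200, 400, 600, 800 and 1000 U, so a 100 U reduction moves a participant to a tier that is otherwise empty in that cohort. The only data there come from someone selected because of an earlier DLT, who does not represent the population rate that θ stands for. At a scheduled dose, waiting for the cohort to finish brings the denominator to six. At a reduced tier it can stay at one.

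If one event at such a tier triggers removal, the loss is large and permanent. For 500 U, section 7.1 notes that "if the 500 U dose tier was dropped, there would only be 100, 200, 300, and 400 U available", and the investigators would then present an amended plan or discontinue. Section 4.3 gives 300 to 1000 U as the range of interest from animal scaling. If removal is not triggered, the final analysis is still affected: 500 U would be reported above the 0.9 threshold on one participant while 600 U is reported below it.

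**Working it through.** **Inputs.** Prior Beta(0.2, 0.8), limit 0.1 and threshold 0.9 (6.1.2, 7.1); Cohort 1 doses 200/400/600/800/1000 U (6.1.2); reduction of 100 U and withdrawal at a second DLT (6.1.2, 8.1.2). Section 6.1.2 requires more than 0.9 and section 7.1 requires 0.9 or more; this makes no difference to the values below.

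**Formula.** With x DLTs among n, Prob(θ>0.1) is the upper tail at 0.1 of Beta(0.2 + x, 0.8 + n − x).

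**Reproducing the plan's figures.** 1/6 = 0.6292, 2/6 = 0.9196, 3/12 = 0.9151, 4/18 = 0.9220 and 5/24 = 0.9310, all as printed in Table SB1A. One cell differs (3/6, printed .9990, computed 0.9900), with no effect on the boundary. With looks at 6, 12, 18 and 24 and boundaries of 2, 3, 4 and 5 DLTs, the table in 9.2 also reproduces. Scenario 5 gives early stop 0.1898, declared toxic 0.2062 and average N 21.1965.

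**The same formula below six patients.**
- No data: 0.408.
- 1/1: Beta(1.2, 0.8), 0.950, removed.
- 1/2: 0.882, kept. 1/3: 0.815. 1/4: 0.749.
- One DLT plus six DLT-free others, 1/7: 0.575, kept.

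**Example in Cohort 1.** A participant has a DLT at 600 U, moves to 500 U and has a second DLT there.
- 600 U: 1/6 = 0.629, kept.
- 500 U, posterior rule: 1/1 = 0.950, so 500 to 1000 U close.
- 500 U, count rule: one DLT against the two required, so nothing closes. Because a second DLT means withdrawal, one person can add at most one DLT at the reduced tier. One person can therefore never close a reduced tier under the counts.

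The same path reaches 100, 300 and 700 U. It does not reach 900 U in Cohort 1, because 1000 U is the last scheduled dose.

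**Counting unit.** If the DLT at the reduced tier follows one DLT-free round there, counting administrations gives 1/2 = 0.882 (kept). Counting patients still gives 1/1 = 0.950 (removed).

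**How often.** The documents give no within-person repeat probability, so the following is assumed: a share of people are susceptible, with a fixed DLT probability at every dose from an onset dose upward, and nobody else has DLTs. The simulation used four cohorts of six, the allocation rules of 6.1.2, removal checked only at cohort end, and each participant counted once per tier. Entries are the percentage of trials in which 500 U and above close; simulation error is about 1 percentage point.

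| Susceptible; DLT probability; onset | True rate from onset | Posterior at any n, reduced rounds counted | Posterior at any n, reduced rounds not counted | 7.1 counts, reduced rounds counted |
|---|---|---|---|---|
| 5%; 0.8; 300 U | 0.05 × 0.8 = 4% | 66% | 3% | 3% |
| 5%; 0.8; 400 U | 4% | 36% | 3% | 3% |
| 3%; 0.8; 300 U | 0.03 × 0.8 = 2.4% | 47% | 1% | 1% |
| 5%; 0.5; 300 U | 0.05 × 0.5 = 2.5% | 48% | 1% | 1% |
| 5%; 0.3; 300 U | 0.05 × 0.3 = 1.5% | 28% | below 1% | below 1% |
| 5%; 0.8; 600 U | 4% | 0% | 0% | 0% |

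The last row is zero by construction: closing 500 U needs a DLT at 500 U or below. A closure at 700 U remains possible there.

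Counting administrations instead of patients lowers the first three entries of the posterior column to 57%, 32% and 41%.

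**Hand check of the first row.** The chance of at least one susceptible person among 24 is 1 − 0.95^24 = 0.71. On the starting schedule such a person has a DLT at 400 U (0.8) and then at least one in three rounds at 300 U (1 − 0.2³ = 0.992). Otherwise the DLT comes at 600 U (0.2 × 0.8 = 0.16), followed by at least one in two rounds at 500 U (1 − 0.2² = 0.96). The sum is 0.794 + 0.154 = 0.947, and 0.71 × 0.947 ≈ 0.67, close to the simulated 66%.

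**The case against.** The strongest reply is that the plan already covers this pattern. One DLT at 600 U and one at 500 U in the same cohort is a case of single DLTs at two different doses, where 6.1.2 drops nothing, and the counts in 7.1 agree. That stands as one of the two readings. It does not settle the matter. The counts are introduced as the practical meaning of a table whose smallest row is six patients, while 6.1.2, 7.1, 9.1 and 9.4.1 all state the criterion as the posterior.

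A reader might infer that the plan pools reduced-dose rounds and that this pooling alone closes tiers. The documents do not support that. Inclusion is the natural reading of an unqualified updating rule, but it is nowhere stated. Nor is it sufficient: in the first scenario, with reduced rounds still counted, closure is 3.1% under the 7.1 counts (3.3% without those rounds) and 3.0% if the posterior is applied only from six patients (2.9% without). The large figures need both the posterior at n below 6 and re-challenge data from selected participants. The small-n gap also exists at any tier whose first patient has a DLT.

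A reader might also take 66% as the expected failure rate. It largely restates the assumed 71% chance of enrolling a susceptible person.

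Finally, removing reduced-dose rounds from the removal calculation looks like an easy cure, but it would hide observed events from a safety rule. If two people had DLTs at 600 U and again at 500 U, 600 U would close (2/6 = 0.920), yet 500 U would sit at its prior (0.408) despite 2/2 (0.995), and the allocation rule could send later participants there.

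**Conclusion.** The concern holds as a conflict between two versions of the removal rule below six patients, at tiers that the within-subject reduction itself creates. One version closes the tier and everything above it after one participant's repeat DLT (0.950); the other closes nothing. The treatment of reduced-dose rounds and the counting unit are undefined, and the operating characteristics in 9.2 do not describe this path.

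The posterior values are exact. The frequency is not known: roughly 0% to 66% of trials under the literal reading, against about 1–3% or less under the counts, in scenarios with a true rate of at most 4% per dose. That range rests wholly on the assumed share of susceptible people, their repeat probability and the onset dose. The documents do not support saying that one participant will close the upper range, only that the text leaves this open.

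**What to change.** Reconcile 6.1.2, 7.1 (both the posterior statement and the counts) and 9.4.1 so that one stated rule governs tiers with fewer than six patients. The same text should say how reduced-dose rounds enter A and B, and whether the unit is the patient or the administration. Which stopping rule to adopt is for the sponsor and investigators; none is proposed here.

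In 9.4.1, report Prob(θ>0.1) for each dose from administrations up to and including each participant's first DLT, alongside the figure from all administrations. Tabulate re-challenge outcomes separately, so that repeat DLTs stay visible.

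The cost is a short clarification of the text, one extra table and a second set of per-dose figures. Nothing about data collection changes.
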